5.5.13.2 Suicidal ideation

The eC-SSRS[®] is an assessment instrument that evaluates suicidal ideation and behavior. During an initial assessment it assesses lifetime as well as the recent history suicidality (scheduled at Visit 2-Baseline), and then prospectively monitors ideations and behaviors at subsequent follow-up assessments since the last call (scheduled at Visit 9-Week 48, Visit 13-Week 96, Visit 17-Week 144 and Visit 18-EOT).

The eC-SSRS[®] outcome categories are provided below. Each category has a binary response (yes/no) and are numbered and ordered below for convenience.

- 1 – Wish to be Dead
- 2 – Non-specific Active Suicidal Thoughts
- 3 – Active Suicidal Ideation with Any Methods (Not Plan) without Intent to Act
- 4 – Active Suicidal Ideation with Some Intent to Act, without Specific Plan
- 5 – Active Suicidal Ideation with Specific Plan and Intent
- 6 – Preparatory Acts or Behavior
- 7 – Aborted Attempt
- 8 – Interrupted Attempt
- 9 – Actual Attempt (non-fatal)
- 10 – Completed Suicide

Furthermore, **self-injurious behavior without suicidal intent** is also an eC-SSRS[®] outcome (although not suicide-related) and has a binary response (yes/no). (Q07a)

The initial assessment has a lifetime and a recent history assessment. The recent history covers the last 1 month for suicidal ideation, and the last 3 months for suicidal behavior. Recent history questionnaire questions are only assessed for outcome categories with corresponding lifetime outcome question answered as yes. If the lifetime assessment for an outcome category is 'No', also the corresponding recent history outcome is considered 'No' for analysis.

Scoring: Scores are created at each assessment as follows:

- **Suicidal Ideation Score:** The maximum suicidal ideation category (1–5 on the eC-SSRS[®]) present at the assessment. Assign a score of 0 if no ideation is present.
- **Suicidal Behavior Score:** The maximum suicidal behavior category (6–10 on the eC-SSRS[®]) present at the assessment. Assign a score of 0 if no behavior is present.

A subject with multiple reported outcomes for suicidal ideation and suicidal behavior will be summarized under the worst reported outcome (i.e., max[1–5] and max[6–10], respectively).

The following definitions will be used:

- **Suicidal ideation:** A “yes” answer to any one of the five suicidal ideation questions (Categories 1–5) on the eC-SSRS[®]. Taken from the ‘Reported most severe ideation level’.
- **Suicidal behavior:** A “yes” answer to any one of the five suicidal behavior questions (Categories 6–10) on the eC-SSRS[®].
- **Suicidal ideation or suicidal behavior**
- **Serious suicidal ideation (score ≥ 4) or suicidal behavior**

The definitions above will be defined at any time in the period from study treatment start up to EOT + 15 days*, for pre-treatment lifetime, and for pre-treatment recent history.

Shifts from baseline (worst outcome from pre-treatment recent history) to the worst outcome up to EOT + 15 days will be derived using the following categories: No ideation (score 0), non-serious suicidal ideation (score 1–3), serious suicidal ideation (score 4–5), suicidal behavior (score 5–10).

* Only post-baseline assessments after study treatment start date from a ‘since last call’ (i.e., not from a lifetime) questionnaire are considered for the analysis.

Baseline is defined as last available recent history result (maximum score) up to study treatment start date, i.e., pre-treatment recent history result.

Lifetime (pre-treatment) is defined as any event (worst outcome) in recent history and lifetime evaluation(s) up to study treatment start date.

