2 STUDY DESIGN AND FLOW

This is a prospective, multicenter, randomized, double-blind, parallel-group, add-on, placebo-controlled, Phase 3, superiority study. The study is designed to compare the efficacy, safety, and tolerability of add-on therapy with ponesimod 20 mg vs placebo in adult subjects with active relapsing multiple sclerosis (RMS) who are treated with dimethyl fumarate (DMF; Tecfidera[®]).

It was planned to randomize approximately 600 subjects who had been receiving DMF twice daily for at least 6 months in a 1:1 ratio to ponesimod 20 mg or placebo (approximately 300 subjects per

arm). Randomization is stratified by baseline Expanded Disability Status Scale (EDSS) score ($EDSS \leq 3.5$, $EDSS > 3.5$).

At the time of the decision to terminate the study, a total of 136 subjects had been randomized at 54 sites (randomized subjects) in 17 countries in North America, and Eastern and Western Europe regions.

Following the decision to terminate the study:

[figure not shown]
- Subjects in screening at the time of the announcement were required to be screen failed;
- Subjects on study treatment were required to perform the End-of-Treatment (EOT) visit within 8 weeks and the follow-up visits;
- Subjects in the post treatment observation period (PTOP) were required to perform the Visit 18A within 4 weeks.

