9.9.7 Columbia Suicide ideation or behavior

Suicidal Ideation, Suicidal Behavior or Self-Injurious Behavior without Suicidal Intent will be listed for each patient, at each assessment visit on the SCR. Events occurring during the period up to EOT + 15 days (treatment-emergent period) will be flagged.

Number (%) of subjects with suicidal ideation (overall and by category), suicidal behavior (overall and by category), suicidal ideation score ≥ 4 or suicidal behavior and/or self-injurious behavior without suicidal intent will be tabulated by treatment group up to EOT + 15 days (worst outcome). Analyses will be based on subjects in the SAF who have at least one treatment-emergent eC-SSRS[®] measurement available.

For subjects who have in addition a baseline eC-SSRS[®] assessment available shifts from baseline (maximum score from pre-treatment recent history) to the worst reported outcome (the maximum score) up to EOT + 15 days will be tabulated by treatment group to demonstrate any changes in Suicidal Ideation and Suicidal Behavior score categories.

All eC-SSRS[®] data will be presented in a listing on SCR.

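### The eC-SSRS tables apply an EOT + 15 day window to a look-back questionnaire, so a late EOT call can be left out although most of its recall period may be on drug

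*SAP*

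**What the plan says.** **Instrument (SAP 5.5.13.2).** After the baseline assessment the eC-SSRS "prospectively monitors ideations and behaviors at subsequent follow-up assessments since the last call". Post-baseline calls are "scheduled at Visit 9-Week 48, Visit 13-Week 96, Visit 17-Week 144 and Visit 18-EOT". Each outcome category is a yes/no answer. The SAP describes no dates for events within a call.

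**Window (SAP 5.5.13.2).** "The definitions above will be defined at any time in the period from study treatment start up to EOT + 15 days". The footnote to that sentence begins "Only post-baseline assessments after study treatment start date from a" look-back questionnaire, so at the start of the window the unit selected is the assessment.

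**Table and flag (SAP 9.9.7).** "Analyses will be based on subjects in the SAF who have at least one treatment-emergent eC-SSRS" measurement available. The shift table uses the same subjects if they also have a baseline assessment. For the listing, "Events occurring during the period up to EOT + 15 days (treatment-emergent period) will be flagged". All eC-SSRS data are listed on the screened set.

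**EOT (SAP 5.3.1.1 and 11.1).** EOT is the latest end date in the study drug logs, that is, last intake and not the EOT visit.

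**EOT visit timing.** SAP Table 3 gives a window of + 7 days. Attachment 1, Section 3.2, codes a visit more than 7 days after discontinuation as a deviation (PD_MM.261, PD_MM.262).

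**The concern.** A cut-off in days after last intake suits a measurement that describes the day it was taken, such as an ECG or a blood sample. A look-back questionnaire describes an interval that may reach back most of a year. If the cut-off is applied to the day of the call, a call a few days too late loses the whole interval, including every day on treatment.

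No later scheduled call recovers it. Section 5.5.13.2 lists no eC-SSRS at the FU visit, and the post-treatment observation schedule (Table 4) has no eC-SSRS row. At stake are the numerator, denominator and shift counts of a safety table in a trial of 136 randomized subjects, where one omitted positive answer could be visible.

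**Working it through.** The SAP gives no figure on this point to reproduce. The check sets the call schedule against the window.

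**1. Which reading applies?**
- For call date: the footnote in 5.5.13.2 selects assessments, and 9.9.7 counts measurements.
- Against: 9.9.7 flags events occurring in the period, and the assessment-date rule in 5.5.1 names only ECG, vital signs and laboratory data.
- Yes/no answers with no described event date cannot be placed as events within the period. Call date is the reading that can be programmed from the text, but it is an inference.

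**2. When is an EOT call lost?**
- Planned visit: at most 7 days after last intake. Cut-off: 15 days. Slack: 15 − 7 = 8 days, so an EOT call on schedule is always kept.
- First lost day: EOT + 16, which is 16 − 7 = 9 days beyond the visit window. A visit 8 to 15 days after last intake is a deviation but loses nothing.

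**3. How much of a lost recall period was on treatment?** Let g be the days from the previous call to last intake and d the days from last intake to the call. For a previous call made on treatment, the on-treatment share is g / (g + d).

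| Gap g (days) | d (days) | Share on treatment |
|---|---|---|
| 336 (48 weeks, the longest scheduled gap) | 16 | 336/352 = 95% |
| 168 (24 weeks) | 16 | 168/184 = 91% |
| 28 (4 weeks, illustration) | 16 | 28/44 = 64% |

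In the first row, 351 of the 352 days lie inside the EOT + 15 window. The share exceeds one half whenever g is larger than d.

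**4. When does the subject leave the table?** Only if no earlier call falls in the window, in practice when treatment stopped before the Week 48 call. Illustration: last dose on day 280 (Week 40) and the EOT call 20 days later. Then 280 of 300 days since first dose (93%) were on treatment. Recall here starts at the baseline call, before first dose. The pre-randomization period lasts up to 45 days (SAP 2.1.1), so the share of the full recall is at least 280/(45 + 280 + 20) = 280/345 = 81%. A subject with an earlier in-window call stays in the denominator and loses only the last interval.

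**5. How do other SAP rules treat similar cases?**
- Section 4.1 shortens the protocol's 30-day treatment-emergent period to 15 days. A call at EOT + 16 to EOT + 30 would have been inside the longer period.
- Section 12.3 counts an adverse event with no onset date as treatment-emergent.
- The first look-back call already includes the days between baseline and first dose, so some off-drug recall is accepted at that end.

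**The case against.** The strongest reply is that the SAP nowhere says a late call is excluded. Its wording on events occurring in the period can be read the other way. That stands: the defect is an unstated rule whose likeliest implementation is a poor one. The SAP is also silent on whether the vendor data hold event dates. If they do, events could be placed directly, but the text gives no rule for doing so.

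Also standing: an EOT visit in its window loses nothing, late results remain in the listing, and suicidality reported as an adverse event is classified by its own onset date under 5.5.1. The tables are descriptive, in a synoptic report of a terminated study.

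Three stronger readings are tempting but unsupported:
- **Termination made late calls common.** A reader might infer this from "Subjects on study treatment were required to perform the End-of-Treatment (EOT) visit within 8 weeks and the follow-up visits". That limit follows the termination decision and is not tied to last intake. Nothing says drug was stopped well before the visit.
- **Every late call removes a subject.** This holds only without an earlier in-window call.
- **The loss is concentrated in early stoppers or differs between arms.** The SAP gives no count of late EOT calls, overall or by arm, and says nothing on who attends late.

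A fair objection to a general overlap rule is that it has no upper limit. A first call long after last intake could be counted although its recall was mostly off drug. The fix is therefore confined to the EOT call.

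**Conclusion.** The point holds as a mismatch between window and instrument, with an ambiguous rule. Under selection by call date, an EOT call at EOT + 16 or later drops out of the summary table, the shift table and the treatment-emergent flag, although up to 336 of 352 recalled days (95%) may be on treatment. The size for a single subject follows from the schedule. The number affected cannot be derived from the document and may be zero.

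The conclusion assumes that calls are placed by date and that answers are undated; the SAP does not state either outright. The primary and secondary efficacy analyses are untouched. This is an inexpensive improvement to a safety table, and it also removes the ambiguity.

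**What to change.** Add one rule to SAP 5.5.13.2 and refer to it in 9.9.7:

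- The Visit 18 (EOT) look-back assessment counts as treatment-emergent when its recall period, from the previous call to this one, overlaps study treatment start to EOT + 15 days, even if the call itself is later than EOT + 15 days.
- It enters the numerator, the denominator and the shift table, and carries the treatment-emergent flag in the listing.
- A footnote gives, by arm, the number of such late calls and their days after last intake.

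Calls made by EOT + 15 days are unaffected. The cost is a sentence in each section and a small programming change. The downside is that some off-drug days enter the recall of late calls, more so when the previous call was recent. The footnoted days after last intake show the reader how late these calls were.

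### The eC-SSRS shift categories in SAP 5.5.13.2 overlap at score 5, so ideation score 5 without behavior could be tabulated as suicidal behavior

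*SAP*

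**What the plan says.** SAP section 5.5.13.2 numbers the eC-SSRS outcomes 1 to 10. The last ideation item is "5 – Active Suicidal Ideation with Specific Plan and Intent" and the first behavior item is "6 – Preparatory Acts or Behavior". Two scores follow from this numbering:

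- The ideation score is "The maximum suicidal ideation category (1–5 on the eC-SSRS"), or 0 if there is none.
- The behavior score is "The maximum suicidal behavior category (6–10 on the eC-SSRS"), or 0 if there is none.

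Suicidal behavior is then defined as a positive answer to "any one of the five suicidal behavior questions (Categories 6–10").

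Later in the section the shift-table categories are listed. The lower two are "No ideation (score 0), non-serious suicidal ideation (score 1–3"), and the upper two are "serious suicidal ideation (score 4–5), suicidal behavior (score 5–10").

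Section 9.9.7 uses these categories. For subjects who also have a baseline assessment, it tabulates by treatment group the shift from the maximum score in the pre-treatment recent history to the maximum score up to 15 days after end of treatment. The stated aim is "to demonstrate any changes in Suicidal Ideation and Suicidal Behavior score categories".

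**The concern.** Score 5 sits in two shift categories, and one of them contradicts the section's own definition of behavior. The sentence matters because it is the only place where the SAP defines the shift categories, and section 9.9.7 gives no tie-break.

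If a programmer pools the two scores into one maximum and resolves the tie toward the worse category, a subject with a plan and intent but no act would appear as having suicidal behavior. Two kinds of error could follow in the shift table:

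- A change from 4 at baseline to 5 on treatment, which stays within serious ideation under the section's definitions, could appear as a new shift to behavior.
- A change from 5 at baseline to 6–10 on treatment, which is a real move from ideation to behavior, could appear as no shift.

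The shift table could then also disagree with the incidence table planned in the same section, where behavior follows the 6–10 definition. For a sensitive safety outcome in a study that stopped at 136 randomized subjects, a single wrong cell would draw attention.

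**Working it through.** No sample-size or error-rate figure is involved. The check is whether the categories partition the possible scores.

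**Inputs (all from SAP 5.5.13.2, with the use of the maximum score from 9.9.7)**

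- Shift categories as stated: 0; 1–3; 4–5; 5–10.
- Ideation score: any of 0, 1, 2, 3, 4, 5 (6 values).
- Behavior score: any of 0, 6, 7, 8, 9, 10 (6 values).
- Behavior as defined in the section: 6–10 (5 items).

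**Step 1. Count the assignments.** There are 11 scores from 0 to 10. The stated categories hold 1 + 3 + 2 + 6 = 12 assignments, one too many.

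| Score | Category as stated | Category with behavior = 6–10 |
|---|---|---|
| 0 | none | none |
| 1–3 | non-serious ideation | non-serious ideation |
| 4 | serious ideation | serious ideation |
| 5 | serious ideation **and** behavior | serious ideation |
| 6–10 | behavior | behavior |

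With 6–10 the count is 1 + 3 + 2 + 5 = 11. Every score has exactly one category and none is left out.

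**Step 2. Find which subjects are affected.** There are 6 × 6 = 36 pairs of ideation and behavior score. On a pooled maximum, any behavior gives at least 6, so the maximum equals 5 only when ideation is 5 and behavior is 0. Exactly 1 of the 36 pairs is ambiguous. This counts possible patterns and says nothing about how often they occur.

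**Step 3. Follow the ambiguous pair under each way of programming the table.**

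| Programming | Ideation 5, behavior 0 goes to |
|---|---|
| Two separate scores; the behavior range is applied to the behavior score | serious ideation (the behavior score cannot be 5) |
| One pooled maximum, tie resolved to the lower category | serious ideation |
| One pooled maximum, tie resolved to the higher category | suicidal behavior |

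Only the third gives the wrong cell. The reference in 9.9.7 to the maximum score makes pooling a natural choice, and reporting the worst outcome makes the upward tie a natural choice. Neither is prescribed.

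**Step 4. Check the other eC-SSRS displays.**

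- The incidence of ideation and of behavior follows the 1–5 and 6–10 definitions, so it does not use the faulty range.
- The composite of ideation score 4 or more or any behavior includes a subject at 5 whichever label is used, so it does not change.

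**The case against.** The strongest defense is that the text around the slip already resolves it. The item list, the two score definitions, the worst-outcome rule (which takes the maximum separately over 1–5 and over 6–10) and the definition of behavior all agree, and one digit differs. If the two scores are kept separate, the behavior score can never be 5, so 5–10 and 6–10 select the same subjects and nobody is misplaced. All eC-SSRS data are also listed by subject, so a wrong cell could be found against the listing or the incidence table.

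Much of this stands. The intended range can be inferred, and misplacement depends on a programming choice. It does not remove the point, because the faulty sentence is the operative rule for this table, and 9.9.7 speaks of the maximum score without saying how a score with two categories is handled.

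Three stronger readings are tempting and are not supported:

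- **That a subject at 5 will be moved to the behavior row.** Step 3 of the working shows that this happens under only one of three ways of programming the table.
- **That the subject would be counted twice.** The shift runs from one baseline outcome to one worst outcome per subject, and nothing in the SAP provides for placing a subject in two cells.
- **That one such subject would be about 1.5% of an arm.** That figure assumes 136 / 2 = 68 subjects per arm, and 1 / 68 = 1.5%. The SAP gives the planned 1:1 ratio but not the arm sizes. The shift table is also restricted to safety-set subjects with both a baseline and a treatment-emergent eC-SSRS assessment, a number the SAP does not give.

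**Conclusion.** Wrong as written, minor. The shift categories overlap at score 5 and contradict the section's own definition of behavior, and nothing in 9.9.7 settles the overlap.

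The effect is confined to one descriptive table without a test, and within it to subjects whose maximum score at baseline or on treatment is exactly 5. How many there are is unknown and may be none, so no percentage can be attached. That any of them would be misclassified rests on the assumption that the two scores are pooled and the tie is taken upward, which the SAP permits but does not require.

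**What to change.** In section 5.5.13.2, change the last shift category to suicidal behavior with score 6–10, and make the same change in the derivation specification if it repeats the range. The categories 0, 1–3, 4–5 and 6–10 are then mutually exclusive, cover every score and match the other definitions in the section. No tie-break is needed in 9.9.7.

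The cost is one digit in the SAP. No data collection and no other planned analysis is affected. If the table has already been programmed, check how a maximum score of 5 was handled and compare the behavior row with the incidence table and the subject listing.

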5.6 Pharmacodynamic variables

5.6.1 Total lymphocyte counts

The main PD marker is total lymphocyte count, which is measured as part of the hematology test from central laboratory. Absolute and change from baseline counts are derived, as described in Section 5.5.12.

Total lymphocyte counts are further categorized into the following categories:

- $< 0.2 \times 10^9/L$;
- $\geq 0.2 \times 10^9/L - < 0.5 \times 10^9/L$;
- $\geq 0.5 \times 10^9/L - < 0.8 \times 10^9/L$;
- $\geq 0.8 \times 10^9/L - < 1.0 \times 10^9/L$;
- $\geq 1.0 \times 10^9/L$.

For each subject in the SAF, the nadir (i.e., lowest) treatment-emergent lymphocyte value (up to EOT + 15 days) is flagged.

Subjects who have a value after Visit 5 (Week 4) (scheduled or unscheduled) which is both $< 0.5 \times 10^9/L$ and represents a decrease from Week 4 $> 50\%$, and which is maintained at all visits (scheduled or unscheduled) for the next 24 weeks, will be flagged.

For example, if a subject has a value of $0.9 \times 10^9/L$ at Visit 5 (Week 4), then a value of $0.4 \times 10^9/L$ at Visit 6 (Week 12), a value of $0.35 \times 10^9/L$ at Visit 7 (Week 24) and a value of $0.4 \times 10^9/L$ at Visit 8 (Week 36), then the subject will be flagged as meeting the above criterion.

Subjects who have a value after Visit 5 (Week 4) (scheduled or unscheduled) which is both $< 0.5 \times 10^9/L$ and represents a decrease from Week 4 of $> 50\%$, and who discontinue treatment within 24 weeks, will be flagged separately if this decrease is maintained at their remaining study scheduled visits, where EOT and FU are considered to be scheduled visits.

Total lymphocyte counts from central laboratory are flagged for analysis according to their sample dates as 'Baseline', 'Last on treatment' and 'Day-30 follow-up' following the rules described in Section 5.5.1 and Section 11.4.

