5.5.12 Laboratory

Laboratory tests will be performed at Visit 1 (Screening), Visit 2 (Baseline), Visit 4 (Week 2), Visit 5 (Week 4), Visit 6 (Week 12) and every 12 weeks thereafter up to Visit 18 (EOT), and at Visit 20 (FU) and, if applicable, at all corresponding visits in the PTOP. Unscheduled laboratory tests may be performed at any time during the study (Visits U1, U2, U3, etc.).

Additional lymphocyte count measurements will be performed every 4 weeks up to Week 24.

Safety laboratory samples are centrally analyzed by Covance and the results are electronically transferred to Actelion. In exceptional cases, the protocol allows the utilization of local laboratories. Local laboratory analysis results are entered in the eCRF with some exceptions for blinding reasons (e.g., lymphocytes are not entered in the eCRF, see protocol). Quantitative results from local laboratories are not summarized (i.e., not included in summary statistics or graphical representations). Qualitative results like (marked) abnormality categorization, liver test elevation categories, etc. are derived from local laboratory data and summarized together with qualitative results derived from central laboratory data.

Safety laboratory hematology, clinical chemistry and urinalysis comprise the following parameters planned as per protocol:

Hematology: Red blood cell count, Total and differential WBC counts (basophils, eosinophils, lymphocytes, monocytes, neutrophils, band forms), Platelet count, Hemoglobin, Hematocrit.

Liver function tests and coagulation: International normalized ratio (INR), alanine aminotransferase (ALT), aspartate aminotransferase (AST), (alkaline phosphatase) AP, total bilirubin (TBIL).

Clinical chemistry (excl. liver tests): Lactate dehydrogenase, Creatinine, creatinine clearance (calculated by the central laboratory using Cockcroft-Gault), Blood Urea Nitrogen, Urate, Glucose, Total cholesterol, Triglycerides, Sodium, potassium, chloride, calcium, Total protein, albumin, C-reactive protein.

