7.1.2 Full analysis set

The full analysis set (FAS) includes all randomized subjects who were treated with at least one dose of study treatment and have at least one post-baseline efficacy assessment.

- In order to preserve the randomization, subjects will be evaluated according to the treatment they have been randomized to (which may be different to the treatment they have received) and stratum information used for randomization as recorded in the IVRS system (which may be different to the information available on the eCRF after data validation);
- Unless otherwise stated, all available efficacy data for the primary and secondary endpoints up to the EOS visit [see Section 11.4] will be included in the analysis, regardless of study treatment discontinuation and/or switches to alternative MS treatments.

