9.10 Analysis of pharmacodynamic variables

9.10.1 Total lymphocyte counts

Descriptive analyses of lymphocyte data are described in Section 9.9.5. Only lymphocyte counts from central laboratory, irrespective of whether obtained at a scheduled or unscheduled visit, are included in any of the below described analyses.

For each subject in the SAF, the nadir (i.e., lowest) treatment-emergent lymphocyte value (up to EOT + 15 days) is summarized by means of frequency counts and percentages based on the categories specified in Section 5.6.

Frequency counts and percentages will be presented for the number of subjects with:

- Total lymphocyte counts $< 0.5 \times 10^9/L$ and $> 50\%$ decrease from baseline at Week 4, maintained at all visits for the next 24 weeks, where the denominator for percentages is the number of subjects with a total lymphocyte count at all scheduled visits for the next 24 weeks;
- Total lymphocyte counts $< 0.5 \times 10^9/L$ at any visit after Week 4 and $> 50\%$ decrease from Week 4, maintained at all visits for the next 24 weeks, OR total lymphocyte count $< 0.5 \times 10^9/L$ at any visit after Week 4 and $> 50\%$ decrease from Week 4, discontinuing for any reason within 24 weeks, with decrease maintained for remaining scheduled study visits, where the denominator for percentages is the number of subjects with a total lymphocyte count $< 0.5 \times 10^9/L$ and $> 50\%$ decrease from Week 4 at any visit after Week 4.

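### The first sustained-lymphopenia flag and the second row of its table put no on-treatment limit on the low count that starts the episode

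*SAP*

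**What the plan says.** Section 5.6.1 defines three lymphocyte variables that matter here.

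- **Nadir.** It is explicitly treatment-emergent: "the nadir (i.e., lowest) treatment-emergent lymphocyte value (up to EOT + 15 days) is flagged".
- **First flag (sustained for 24 weeks).** It takes "Subjects who have a value after Visit 5 (Week 4) (scheduled or unscheduled) which is both" below 0.5 × 10^9/L and more than 50% below the Week 4 count, "and which is maintained at all visits (scheduled or unscheduled) for the next 24 weeks, will be flagged". No EOT or EOT + 15 days limit is stated.
- **Second flag (discontinuers).** It takes the same low count in subjects "and who discontinue treatment within 24 weeks, will be flagged separately if this decrease is maintained at their remaining study scheduled visits".

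Section 9.10.1 tabulates two rows besides the nadir. Row 1 is worded around a low count at Week 4. Row 2 joins the two flags: more than 50% "decrease from Week 4, maintained at all visits for the next 24 weeks, OR total lymphocyte count" below the threshold with discontinuation within 24 weeks. The row 2 denominator is every subject with a qualifying count at any visit after Week 4. The only general data rule in that section is that counts come from the central laboratory.

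Laboratory tests continue after study drug is stopped: Section 5.5.12 schedules them, "if applicable, at all corresponding visits in the PTOP", and Table 4 marks lymphocytes at every PTOP visit.

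**The concern.** The nadir and the first flag stand next to each other and describe the same marker. One is confined to the treatment-emergent window and the other is not. A programmer who follows the text would pass PTOP counts into the flag and into row 2. A subject could then appear as a sustained-lymphopenia case on study treatment although every low count came well after the last dose, for instance under a different MS drug.

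The purpose of such a table is to describe lymphopenia under the add-on combination, and an episode that begins off study drug does not inform that. Because the row 2 denominator contains only subjects who already had a qualifying low count, it is likely to be small, and one misplaced subject changes the percentage visibly.

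**Working it through.** The SAP gives no figure to reproduce. The check is whether another rule supplies the missing limit, whether the situation can arise, and what one case does to the table.

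**1. Does another rule supply the limit?**

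- Section 5.5.1 defines treatment-emergent laboratory values (study treatment start to end date + 15 days), but a definition applies only where an analysis calls on it.
- Section 9.9.5 calls on it for the by-visit summaries, the marked abnormalities and the liver test abnormalities. Sections 9.9.3, 9.9.4, 9.9.6 and 9.9.7 do so for ECG, vital signs, spirometry and suicidality. Section 9.10.1 does so for the nadir.
- Neither the first flag nor row 2 calls on it.

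**2. Can the situation arise?**

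- Section 2.1.1: the PTOP runs on the 12-weekly schedule to Week 156 or 60 weeks after the last randomisation, whichever is first.
- Section 1: enrolment began in March 2017 and had run 2.5 years by the September 2019 data monitoring meeting, about 2.5 × 52 = 130 weeks. An early entrant who stopped study drug early could therefore have 24 weeks of PTOP counts.
- Section 7.1.2 foresees efficacy follow-up "regardless of study treatment discontinuation and/or switches to alternative MS treatments". It sets no rule for lymphocytes, but it shows that switching was expected.

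**3. One illustrative subject (assumed values, × 10^9/L).** Week 4 count 1.2; last dose at Week 20; no qualifying count before Week 48; PTOP counts as below.

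| Visit | Count | Fall from Week 4 |
|---|---|---|
| Week 48 | 0.45 | 1 − 0.45/1.2 = 62.5% |
| Week 60 | 0.40 | 1 − 0.40/1.2 = 66.7% |
| Week 72 | 0.42 | 1 − 0.42/1.2 = 65.0% |

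All three counts are below 0.5, all three falls exceed 50%, and Week 72 − Week 48 = 24 weeks. EOT + 15 days falls shortly after Week 22, so every low count lies outside the treatment-emergent window.

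- First flag as written: met.
- Nadir: none of these counts is eligible.
- Second flag: not met, because treatment had stopped before the first low count.
- First flag with an onset limit of EOT + 15 days: not met.

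**4. Effect on row 2.** Assume four subjects in a group have a qualifying count on drug and one is sustained: 1/4 = 25%.

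- Add one PTOP-onset case that is sustained: (1 + 1)/(4 + 1) = 2/5 = 40%.
- Add one PTOP-onset case that is not sustained: 1/(4 + 1) = 1/5 = 20%.

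The second case needs only a single low PTOP count, not 24 further weeks of follow-up.

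**The case against.** The best defence is that the first flag was meant for subjects still on study drug. Discontinuers are flagged separately, the worked example in 5.6.1 uses Visits 6, 7 and 8 rather than their PTOP counterparts 6A, 7A and 8A, and the extra scheduled visits it names are EOT and FU. That may well be the intention, but it is not the rule: the text admits any scheduled or unscheduled value after Week 4, and the neighbouring nadir shows that the authors state the limit when they want it.

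A second defence is that cases will be few. Enrolment was slow, and at termination PTOP subjects had to complete Visit 18A within 4 weeks. This limits sustained PTOP cases, but not entry to the denominator. Safety listings also flag treatment-emergent values (Section 9.2), so a PTOP-onset case could be found there. The table itself would still contain it.

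Several objections to a wider claim stand in full:

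- A reader might infer that both flags and both rows are open. The second flag requires discontinuation within 24 weeks of the low count, so on the ordinary reading that count comes first. Row 1, as written, is tied to Week 4.
- A reader might say that the cases are charged to the randomised arm. The safety analysis set groups subjects by treatment actually received (Section 7.1.3).
- A reader might argue that false cases gather on placebo and mask an excess on ponesimod, since a PTOP count of 0.40 is a 69% fall from a Week 4 count of 1.3 (1 − 0.40/1.3) but only a 33% fall from 0.6 (1 − 0.40/0.6). Both Week 4 values are invented, and the SAP offers nothing to show how PTOP entry or switching differs between groups.

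**Conclusion.** The defect is real but confined to the first flag in 5.6.1 and to the first limb and the denominator of row 2 in 9.10.1. As written, these can count an episode that begins wholly after study drug was stopped, and one such subject can shift the row 2 percentage up or down. The 25% to 40% or 20% example rests on an assumed 1 of 4.

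The overall size and the direction across groups cannot be determined. The SAP does not say how many subjects entered the PTOP, changed MS treatment, or had 24 weeks of counts there. An expected number of false flags could be built from guesses. For 68 placebo subjects (136/2, assuming equal groups), taking assumed proportions for PTOP entry, switching, 24 weeks of further counts and meeting the thresholds, it runs from 68 × 0.15 × 0.2 × 0.3 × 0.3 = 0.18 to 68 × 0.3 × 0.4 × 0.6 × 0.7 = 3.4. That spread reflects the guesses, not the document.

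The table is descriptive and no hypothesis test depends on it. The correction is still worth making because the denominator is likely to be small and the remedy is simple.

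**What to change.** - **Section 5.6.1, first flag:** state that the first qualifying count of the episode must be treatment-emergent, from study treatment start to EOT + 15 days inclusive, as for the nadir. Counts after EOT still serve to judge whether that episode persists for 24 weeks.
- **Section 9.10.1, row 2:** apply the same onset condition to the numerator, and restrict the denominator to subjects with at least one treatment-emergent qualifying count after Week 4.
- **Leave alone:** the second flag and row 1 do not need this limit.

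It would go too far to discard all counts taken after another MS drug is started. That would change how persistence is judged for episodes that began on study drug, and it would leave subjects who switch within 24 weeks without a classification.

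Cost: a sentence in each section and one date condition in the program. No new data are needed.
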